10. ANALYSIS PLAN

10.1. Analysis Data Sets

All subjects who are enrolled in the study will be evaluated for safety. Efficacy analyses will be performed based on data from those eyes with uncomplicated LASIK surgery.

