6. OBJECTIVE(S)

To determine the percentage of subjects satisfied (Completely Satisfied or Very Satisfied) with vision after Phoreides Planned Contoura LASIK.

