7. SUBJECTS

7.1. Subject Population

Eligible test subjects will be 21 to 39 years of age or older and who are interested in and appropriate candidates for LASIK.

A total of 104 eyes of 52 subjects at one site will be enrolled. Both eyes of a subject must be enrolled. Subjects must meet the inclusion criteria. Prior to enrollment, subjects will be provided information on the study and asked to sign a patient information and consent form to participate. The patient information and consent form will be approved by an appropriate ethics committee.

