7.2. Inclusion Criteria

Subjects are eligible for the study if they meet the following criteria:

Note: Ocular criteria must be met in both eyes.

- Appropriate candidate for uncomplicated bilateral LASIK surgery
- Gender: Males and Females.
- Age: 21 to 39 years of age.

- Refractive error range SE refractive errors up to 0.00 to -9.00 D with maximum cylinder up to 3.00 D and sphere \leq -8.00 D.
- If currently wearing contact lenses:
 - Soft CTL wearers discontinue for minimum 3 days
 - o RGP CTL wearers discontinue for 1 month per decade of wear
 - Stable refraction (2 consecutive manifest refractions within 0.25 SE)
 - Stable K readings (2 consecutive K readings in 2 consecutive visits)
- Residual bed thickness 250µm or greater
- Willing and able to comply with scheduled visits and other study procedures.
- Pre-surgery BCDVA of 20/20 (0.00 logMAR) or better in each eye.

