8. STUDY DESIGN

8.1. Study Design

This study is a single site, single-arm, prospective, observational study of subject satisfaction, after successful bilateral LASIK surgery. Subjects will be assessed pre-operatively, operatively and at 1 week, 1 month, and 3 months post-operatively. Clinical evaluations will include measurement of visual acuity, manifest refraction, and topography, aberrometry, and administration of the OSDI and PROWL questionnaires.

The primary outcome measure will be the percentage of subjects satisfied (Completely Satisfied or Very Satisfied) with vision after Phorcides Planned Contoura LASIK based on PROWL Questionnaire preoperative vs postoperative (question #1 only).

Secondary outcome measures are as follows:

• Percentage of eyes with post-op spherical equivalent within +/- 0.50 D.

Exploratory outcome measures are as follows:

- Preoperative and postoperative higher order aberrations (spherical aberration and coma).
- Preoperative and postoperative responses on the PROWL questionnaire (Q2-Q33).
- Preoperative and postoperative OSDI scores.
- Correlation of postoperative OSDI score and responses on the postoperative PROWL questionnaire (Q1).

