8.2. Methods Used to Minimize Bias

As a single-arm study there is no expected bias. Patient selection will be based on the patient's interest and the surgeon's opinion as to whether they are a suitable candidate for LASIK.

The measurement of visual acuity will be conducted in a systematic fashion to minimize bias. Individuals conducting visual acuity measures will be instructed to perform the same testing in the same fashion for all subjects, with the same level of encouragement to subjects. Questionnaire instructions will be provided to all patients in a similar manner.

All data collection will be completed through provided Case Report Forms (CRFs) or computer files generated by automated test equipment. All site personnel involved in the study will be trained in regard to conducting study-specific procedures.

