10.2. Statistical Methodology

A summary of the data will be prepared for all measurement time points.

For variables measured on a continuous scale, these summaries will include the sample size, as well as the mean, standard deviation, median, minimum, and maximum. For variables measured on a categorical scale, summaries will provide the number and percentage of subjects in each category. These summaries will be provided for all eyes completing the study.

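### The plan does not settle which subjects give the headline satisfaction percentage: Section 10.1 keeps only eyes with undefined uncomplicated surgery, Section 10.2 uses a different set, and no all-treated efficacy analysis is planned

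*Combined protocol and SAP*

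**What the plan says.** Section 6 gives the objective: "To determine the percentage of subjects satisfied (Completely Satisfied or Very Satisfied) with vision after Phoreides Planned Contoura LASIK". It carries no limit to operations that went well. Sections 3 and 8.1 make the primary outcome a percentage of subjects, based on PROWL question 1.

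Section 10.1 sets out two populations. For safety: "All subjects who are enrolled in the study will be evaluated for safety". For efficacy: "Efficacy analyses will be performed based on data from those eyes with uncomplicated LASIK surgery". Section 10.2 then says of the descriptive summaries: "These summaries will be provided for all eyes completing the study".

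Other sections also bear on who is counted:

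- Section 7.1: "Both eyes of a subject must be enrolled".
- Section 7.2 requires: "Appropriate candidate for uncomplicated bilateral LASIK surgery". This is the only other use of the word uncomplicated in this sense, and it is a judgement made before surgery.
- Section 8.1 describes an "observational study of subject satisfaction, after successful bilateral LASIK surgery".
- Section 9.2.2 allows performance data to be left out when surgery was not successfully completed, but does not require it.
- Section 7.3 lets the investigator rule a patient nonevaluable on medical evidence. It also allows, without requiring, exclusion of effectiveness data after a pregnancy, for a stated reason.
- Section 8.2: "As a single-arm study there is no expected bias".

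**The concern.** With no control arm, the percentage satisfied is the whole result, and it depends on who is in the denominator. Section 10.1 removes eyes according to something that happens during or after treatment. If complications go with lower satisfaction, the reported figure will be higher than the one a prospective patient would face, and the objective reads as describing that patient. A single-arm design does not remove this route to bias, whatever Section 8.2 says.

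There are three gaps in the rule itself. The key term is undefined. An eye-level rule is applied to a subject-level outcome, so a subject with one complicated eye is neither clearly in nor clearly out. And Sections 9.2.2, 10.1 and 10.2 describe three different selections without saying which one yields the primary percentage.

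**Working it through.** **Which set?** The relevant rules side by side:

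| Section | Who is counted or removed | Unit | Nature of the rule |
|---|---|---|---|
| 6 | Satisfied after the procedure | Subject | No restriction |
| 10.1 | Kept if surgery uncomplicated | Eye | Firm, but term undefined |
| 10.2 | Kept if study completed | Eye, though categories are counted in subjects | Firm, no complication filter |
| 9.2.2 | May be removed if surgery not successful | Subject | Discretionary |
| 7.3 | May be removed if nonevaluable or pregnant | Subject | Discretionary |

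A subject with a complicated eye who reaches Visit 5 is outside the 10.1 set for that eye and inside the 10.2 set. Under 9.2.2 the same subject could fall either way. No text says which set the primary percentage comes from, and none of the sets is everyone treated.

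**How large could it be?** The plan gives no figure to reproduce here: no complication rate, no expected percentage satisfied and no size for the efficacy set. The sample size of 46 pairs in Section 11 concerns a mean difference in points and does not bear on this question. The one usable input is 52 subjects and 104 eyes (Section 7.1). The rest is assumption: all 52 are treated and answer at Visit 5, *k* are excluded, about 90% of those kept (*x*) are satisfied, and *s* of the excluded are satisfied.

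Restricted percentage = *x*/(52 − *k*). All-treated percentage = (*x* + *s*)/52. Shift = restricted minus all-treated.

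| *k* | Restricted | *s* | All-treated | Shift (points) |
|---|---|---|---|---|
| 1 | 46/51 = 90.2% | 0 | 46/52 = 88.5% | +1.7 |
| 1 | 46/51 = 90.2% | 1 | 47/52 = 90.4% | −0.2 |
| 3 | 44/49 = 89.8% | 0 | 44/52 = 84.6% | +5.2 |
| 3 | 44/49 = 89.8% | 2 | 46/52 = 88.5% | +1.3 |
| 3 | 44/49 = 89.8% | 3 | 47/52 = 90.4% | −0.6 |

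With no exclusions the shift is zero. If excluded subjects resemble the rest it is about zero. Exact (Clopper-Pearson) 95% intervals are 77.8% to 96.6% for 44/49 and 71.9% to 93.1% for 44/52.

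**Eye against subject.** If three subjects each have one complicated eye, 104 − 3 = 101 eyes remain, but the question 1 denominator could be 49 or 52. For the secondary outcome (within 0.50 D, counted by eye), suppose 95 of the 101 kept eyes succeed: 95/101 = 94.1%. If the three excluded eyes all miss, the all-treated figure is 95/104 = 91.3%, a shift of +2.7. If all three succeed it is 98/104 = 94.2%, a shift of −0.2.

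**Missing answers, a separate matter.** PROWL is scheduled only before surgery and at Visit 5 (Table 15.1), so a dropout is missing data rather than a 10.1 exclusion. For scale, if 52 − 46 = 6 answers were missing and 41 of 46 were satisfied (89.1%), the bounds would be 41/52 = 78.8% and 47/52 = 90.4%.

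**The case against.** The restriction is partly intended and disclosed: Section 8.1 speaks of successful bilateral surgery, and Section 7.2 points the same way. That stands, and it is a reason to keep the uncomplicated set as a supportive analysis. It does not define the term or settle the subject with one complicated eye. Section 7.2 concerns candidacy, not how the operation turned out.

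Three stronger readings are tempting, and the documents do not support them:

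- *The two restrictions stack, so the result describes only uncomplicated completers.* Section 10.2 carries no complication filter. Read plainly, its summaries include complicated eyes that reach the end of the study. Sections 10.1 and 10.2 conflict rather than combine.
- *An unmasked team can pick the denominator freely after seeing the answers.* Section 9.2.2 has adverse events and other problems during surgery noted at the operative visit, and unsuccessful surgery documented in the case report form. Visit 5 comes at 90 ± 20 days. The underlying facts should therefore be on record before the outcome. The remaining discretion lies in the permissive exclusions of 9.2.2 and 7.3 and the nonevaluable ruling in 7.3, none of which has a stated time.
- *The percentage is overstated.* The direction is plausible for complicated surgery, but nothing in the documents shows it, and the assumed range includes zero. No direction is claimed for the pregnancy exclusion.

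It is also fair to say that the largest shift shown is smaller than the sampling uncertainty at this sample size. But the interval around a restricted percentage does not cover the effect of the restriction.

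**Conclusion.** The point holds as a defect in the definition of the analysis set. The efficacy population is selected on an undefined post-surgery condition, by eye for a subject-level outcome. Sections 9.2.2, 10.1 and 10.2 do not agree on who is counted, and no all-treated efficacy analysis is planned although the objective has no such limit.

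The shift in the headline figure runs from −0.6 to +5.2 points, on the assumptions of about 90% satisfied and up to 3 of 52 excluded. The upper end needs three exclusions, all dissatisfied. The plan sets no numeric success threshold, so no planned decision is shown to change. It is worth correcting before analysis because the percentage is the study's main product and the correction is cheap. Confidence is moderate: the textual gaps are clear, the size and direction are not.

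A separate point is that Section 18.3 treats terminated subjects as having completed, while 18.1 ties completion to Visit 5 and the Exit Procedures section records a premature exit as not completed. This affects who enters the 10.2 summaries but is not caused by 10.1.

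**What to change.** - **Primary analysis (10.1).** Report the percentage satisfied on PROWL question 1 at Visit 5 for all subjects in whom laser treatment was performed, regardless of complication. Use one record per subject and an exact confidence interval. Include and flag subjects treated in one eye only. Use all treated eyes for the 0.50 D secondary outcome.
- **Missing answers.** Show how many Visit 5 answers are missing, and give a lower bound that counts them as not satisfied. State whether a questionnaire completed at an early exit examination counts.
- **Supportive analysis.** Keep the uncomplicated set. Define the term from the operative case report form, fix the classification before the Visit 5 questionnaires are reviewed, and leave subjects with one complicated eye out of this set for question 1.
- **Discretion.** Replace the permissive exclusions in 7.3 and 9.2.2, and any post-surgery nonevaluable ruling, with fixed analysis rules. List each exclusion with its reason.
- **Consistency.** Reconcile 9.2.2, 10.1 and 10.2. Separately, reconcile 18.1, 18.3 and the Exit Procedures on completer status for analysis only, leaving the clinical termination rule untouched.

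The cost is wording changes and a little more analysis, with no new visits or instruments. The headline percentage may come out slightly lower.

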10.2. Statistical Methodology

A summary of the data will be prepared for all measurement time points.

For variables measured on a continuous scale, these summaries will include the sample size, as well as the mean, standard deviation, median, minimum, and maximum. For variables measured on a categorical scale, summaries will provide the number and percentage of subjects in each category. These summaries will be provided for all eyes completing the study.

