9.2.3. Postoperative 1 Week

All routine, usual standard of care postoperative measures should be undertaken. In addition, the subject will undergo VA, manifest refraction, slit lamp examination (Section 9.3). Any device deficiencies or adverse events will be monitored.

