9.5. Discontinued Subjects

Discontinued subjects are those who do not have an exit visit or who come into the office to be exited prior to the scheduled final study visit. Subjects may be discontinued from the study at any time if, in the opinion of the investigator, their continued participation in the study poses a risk to their health. The reasons for discontinuation include:

- a. Adverse event;
- b. Lost to follow-up;
- c. Subject decision unrelated to an adverse event;
- d. Protocol violation;
- e. Treatment failure;
- f. Other.

To ensure the safety of all subjects who discontinue prior to Visit 5, investigators should assess each subject and, if necessary, advise them of any therapies and/or medical procedures that might be needed to maintain their health. Any changes in medical health and/or use of concomitant medications should also be captured.

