13.5. Safety Analyses

The type, severity, duration and frequency of reported ocular adverse events will be tabulated. Adverse events will also be summarized for events that were considered treatment-related.

14. GCP, ICH and ETHICAL CONSIDERATIONS

This study will be conducted in compliance with Good Clinical Practices (GCPs), including International Harmonization (ICH) Guidelines, and in general, consistent with the 1996 version of the Declaration of Helsinki. In addition, all applicable local, state and federal requirements will be adhered to.

This study is to be conducted in accordance with Institutional Review Board regulations. The investigator will obtain appropriate IRB/ethics committee approval prior to initiating the study.

The study will be registered with clinicaltrials.gov.

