18. STUDY ENDPOINT CRITERIA

18.1. Patient Completion of Study

If a study patient has completed the final visit (Visit 5) of the study, he/she is considered to have completed the study.

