18.3. Patient Termination

A study patient will be terminated if the study patient develops any severe adverse event that may be related to the study. A study patient will receive appropriate treatment at the discretion of the investigator. Notification of termination will be clearly documented. These study patients are considered to have completed the study and will not be replaced.

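### Section 10.2 limits the summaries at every visit to eyes that complete the study, although 10.1 sets no such condition, so early-visit results of subjects who leave before Visit 5 drop out of the tables

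*Combined protocol and SAP*

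**What the plan says.** Section 10.2 opens with "A summary of the data will be prepared for all measurement time points" and, after listing the statistics, closes with "These summaries will be provided for all eyes completing the study". The closing sentence refers back to the summaries just described, so on a plain reading it covers every visit.

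Other sections bear on who is included:

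- **Section 18.1:** "If a study patient has completed the final visit (Visit 5) of the study, he/she is considered to have completed the study".
- **Section 18.3**, on subjects terminated for a severe adverse event that may be related to the study: "These study patients are considered to have completed the study and will not be replaced".
- **Section 9.5:** "Discontinued subjects are those who do not have an exit visit or who come into the office to be exited prior to the scheduled final" (quote cut short here; the visit meant is Visit 5). Its list of reasons includes adverse event and treatment failure.
- **Section 10.1:** the efficacy set is eyes whose LASIK was uncomplicated, with no completion condition. For safety, "All subjects who are enrolled in the study will be evaluated for safety".
- **Section 13.5:** "The type, severity, duration and frequency of reported ocular adverse events will be tabulated". It plans no table of acuity or slit-lamp results.
- **Exit Procedures (section 9.2):** at premature exit, the study examinations are to be done where possible.

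**The concern.** A 1-week or 1-month table restricted to eyes that later reach Visit 5 describes a group selected on something that had not yet happened. If subjects with a poor early result are more likely to leave, the early tables look better than the operated group did. The plan itself foresees departures of this kind, since 9.5 names adverse event and treatment failure as reasons for leaving.

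The rule also sets aside observations the protocol has asked for, including those gathered at a premature exit visit. And because 10.1 and 10.2 imply different denominators with neither said to govern, two analysts could produce different tables from the same data.

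**Working it through.** **1. The plan's own figure.** Section 11 gives a mean difference of 25, a standard deviation of differences of 50, 90% power, 5% significance and 46 pairs.

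- Standardised effect: 25/50 = 0.5.
- Two-sided normal approximation: (3.2415/0.5)² = 42.03, so 43.
- Exact two-sided paired t-test: 44 pairs (power 90.0%). Power at 46 pairs is 91.3%.
- One-sided versions give 35 or 36 and do not match.

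The stated 46 is reproduced to within 2 pairs. It matters here only as the base for the dropout allowance; nothing in this point changes the sample size.

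**2. The allowance.** 52 − 46 = 6 subjects; 6/52 = 11.5%, or 12 of 104 eyes. Section 11 states no rate or timing. A 10% rate gives 46/0.90 = 51.1, so 52; an 11.5% rate gives 46/0.885 = 51.98, so also 52. The 11.5% is therefore implied, not stated. Section 18.2 replaces subjects who leave before surgery, so I take the allowance to concern operated subjects.

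**3. What is left out for a subject who leaves after 1 month.**

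| Visit | Collected | 10.1 efficacy set (uncomplicated eye) | 10.2 tables |
|---|---|---|---|
| Preoperative | acuity, refraction, slit lamp, fundus, topography, aberrometry, PROWL, OSDI | in | out |
| 1 week | uncorrected acuity, slit lamp; refraction in the visit text but not marked in Table 15.1 | in | out |
| 1 month | acuity, refraction, slit lamp | in | out |
| Early exit, if attended | study examinations where possible | in | out |

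The exception is a subject terminated under 18.3 before Visit 5. That subject is a completer under 18.3, does not meet 18.1, and is discontinued under 9.5.

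**4. How many eyes.** Each leaver removes 2 of 104 eyes (1.9%). Assuming all 52 subjects have both eyes operated without complication and are seen at the visit:

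| Leavers | Eyes in table | Left out |
|---|---|---|
| 1 | 102 | 1.9% |
| 3 | 98 | 5.8% |
| 6 | 92 | 11.5% |

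**5. Direction and possible shift.** The documents give no early-visit results. Assume, for illustration only, that 94 of 104 eyes (90.4%) are within 0.50 D at 1 month. If 12 eyes leave and k of them are out of range, the completer percentage is (94 − (12 − k))/92 = (82 + k)/92.

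- Leaving unrelated to outcome: expected k = 12 × 10/104 = 1.15, giving 83.15/92 = 90.4%, no shift.
- k = 2: 84/92 = 91.3%.
- k = 4: 86/92 = 93.5%.
- k = 6: 88/92 = 95.7%.
- A separate extreme case, three leavers with all six eyes out of range: 94/98 = 95.9%.

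The shift runs from none to about 5 percentage points across these assumed cases. None is a forecast.

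**The case against.** The strongest reply is that little of consequence depends on the sentence. PROWL, OSDI, topography and aberrometry are scheduled only preoperatively and at 3 months, so an early leaver normally has no postoperative value whatever 10.2 says. No sample size or named hypothesis rests on the 1-week and 1-month tables. This stands, and it sets the priority.

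Other parts of the reply also stand:

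- Section 10.1 has no completion condition, so the plan is inconsistent rather than settled on a completer analysis.
- Clinically adverse findings reported as adverse events reach the 13.5 tables, which have no completer limit. A reader might infer that early leavers' examination results appear nowhere; that holds only for results not reported as adverse events.
- Section 18.3 keeps some subjects with bad outcomes in the tables, which limits the bias.
- A fixed cohort has a use: it follows the same eyes across visits.
- Section 10.2 asks for the sample size with continuous summaries, so a reduced denominator would be partly visible.

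None of this removes the selection on a later event in the early tables, or the disagreement between 10.1 and 10.2.

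**Conclusion.** The point holds as a low-priority correction. Read with 18.1, section 10.2 leaves observed preoperative, 1-week and 1-month results of early leavers out of the tables, and it does not agree with 10.1. At the enrolment allowance, up to 12 of 104 eyes (11.5%) are affected per early visit; fewer if some subjects leave before the visit in question, more if dropout exceeds the allowance. Any bias is zero if leaving is unrelated to outcome and favourable if poor early results lead to leaving. The documents do not allow a choice between these.

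Three stronger readings are tempting but unsupported:

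- *The primary result is biased by this rule.* Apart from a questionnaire completed at a premature exit visit, there is no postoperative PROWL value for 10.2 to exclude.
- *The secondary outcome is distorted.* No visit is named for the percentage of eyes within 0.50 D, and nothing makes it a 1-week or 1-month endpoint.
- *The plan expects 11.5% dropout, or data are discarded.* Section 11 gives an enrolment number, not a rate, and the results are omitted from summaries, not deleted.

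The 1-week refraction part also depends on whether the visit text or Table 15.1 governs.

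**What to change.** Replace the last sentence of 10.2 with wording such as: *Summaries at each visit will include all eyes in the applicable section 10.1 analysis set (uncomplicated LASIK for efficacy; all enrolled subjects for safety) with data at that visit, showing the number examined out of the number in the set. Summaries restricted to eyes completing Visit 5 are supplementary.*

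Tying the sentence to the 10.1 sets matters. A rule covering all operated eyes would override the uncomplicated-surgery condition and the provision in 9.2.2 that performance data from unsuccessful surgery may be excluded.

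Also reconcile 18.1, 18.3 and 9.5 on who counts as a completer for analysis, and the 1-week visit text with Table 15.1 on refraction.

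The cost is one replaced sentence and those clarifications, with no new data, visits or subjects. The small downside is that the main tables no longer follow one fixed cohort across visits; the supplementary completer table covers that.
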